6.3. Study Discontinuation

All patients, regardless of the completion or premature discontinuation, should perform the End of Study Visit according to the study flow-chart.

6.4. Screen and Baseline Failures

All potential patients who have signed an informed consent and are screened for enrolment in this study will be listed on the patient Screening Log/Identification List. Reasons for exclusion will be recorded for potential patients who do not enter the study.

A patient who does not fulfil the randomization criteria will be considered as a screen failure. All patient data should be entered in the eCRF including the screen failure data.

A patient will be considered a baseline failure if the patient signs the informed consent, is eligible for randomization but withdraws before the baseline visit.

Based on the investigator evaluation and sponsor prior approval, a non-randomized patient can be re-screened. This re-screening procedure should be documented, the patient should consent again and a new unique and incremental patient Identification (ID) number be allocated.

7. ADVERSE EVENTS (AE) AND SERIOUS ADVERSE EVENTS (SAE)

The investigator is responsible for the detection and documentation of events meeting the criteria and definition of an AE or SAE. During the study, in case of a safety evaluation, the investigator or site staff will be responsible for reporting AEs and SAEs, as detailed in this section of the protocol.

During the screening period, only adverse event related to the screening procedures will be collected.

Any disease progression will be reported in the eCRF both as an adverse event and documented in the efficacy section.

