2.3. Primary Endpoint

The primary endpoint is the incidence of treatment-emergent adverse events in the ABX464 treated Patients versus placebo, categorized by severity.

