6.2. Premature trial discontinuation

A patient can be withdrawn at any time from the study for the following reasons:

Patient's premature trial discontinuation could occur for the following reasons:

- Investigator's decision;
- An Adverse Event or an intercurrent condition that preclude continuation of treatment;
 - Specifically, an increase ≥ 3.0 x ULN in liver transaminases (AST/SGOT and/or ALT/SGPT) or an increase ≥ 2.0 x ULN in Alkaline phosphatase or in total bilirubin requires close observation with repeating liver enzymes and serum bilirubin tests two times weekly and clinical investigation to understand the etiology of this elevation. Frequency of retesting can decrease to once a month if abnormality stabilizes after this initial two weeks of follow-up and if the patient is asymptomatic. Discontinuation of the study treatment should occur if:
 - ALT or AST > 8 xULN
 - ALT or AST > 5 xULN for more than 2 weeks
 - ALT or AST > 3 xULN and total bilirubin > 2 xULN or INR >1.5
 - ALT or AST > 3 xULN with appearance of fatigue, nausea, vomiting, right upper quadrant pain or tenderness, fever, rash, and/or eosinophilia ($>5\%$).
- Worsening of the RA (according to physician evaluation);
- Major protocol violation;
- Withdrawal of consent;
- Administrative reasons from Sponsor.

A patient who prematurely exits the study will not be replaced.

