8.6. Determination of sample size

The primary efficacy endpoint is the rate of subjects meeting the ACR20. This response rate will be compared in subjects who received a given dose of ABX464 or placebo by likelihood ratio chi-square

test. The result of the test will be interpreted in a descriptive manner therefore no adjustment for multiple comparison is applied.

For the sample size assessment, the following assumptions will be made:

- Response rate (ABX464): 0.65
- Response rate (placebo): 0.25

According to literature the ACR20 response rate for ABX464 + MTX treated subjects is expected to be between 50% and 65% while that in the placebo + MTX group is assumed to be approximately 25 to 30% (Xeljanz® Summary of Product Characteristics; ORAL Standard Investigators - N Engl J Med 2012; 367:508-519 August 9, 2012 (8)).

- Type 1 error: 10% two-sided
- Group allocation rate (ABX464 / placebo): 1:1:1

If the above assumptions and definitions hold true with a sample size of 60 subjects receiving two doses of ABX464 or placebo in a ratio of 1:1:1 the study has 84% power to show a difference in response rate between one active study group and placebo.

Subjects who terminates the study prematurely will be considered failures therefore no adjustment for drop-outs is needed.

Primary safety endpoint is the rate of all treatment emergent adverse experiences. The above sample size is sufficient to detect an increase in general treatment emergent adverse experience rate from 10% to 50% with 89% power by likelihood ratio chi-square test on a 10%, two-sided significance level.

If approximately 20 subjects receive ABX464 the study has 88% chance to detect at least 1 specific treatment emergent AE if the underlying rate of occurrence is 1:10.

When the underlying rate of occurrence is around 1:20 the sample size of 40 subjects receiving active treatment is sufficient to observe at least 1 such an event with a probability of 87% in the active treatment group.

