4 STUDY VARIABLES AND COVARIATES

4.1 PRIMARY VARIABLE

The primary variable for statistical comparison between treatment groups will be the incidence of treatment-emergent adverse events in the ABX464 treated Patients versus placebo, categorized by severity.

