11.6 SAFETY ANALYSES

11.6.1 Adverse Events

An overall summary table will be presented (any adverse event, any treatment emergent adverse event (TEAE), any serious adverse event (SAE), death, any grade 3 or higher adverse events from baseline to the end of Study) (*Table 14.3.1.1*). This analysis will be conducted on SAF population.

Primary safety endpoint, the rate of all treatment emergent adverse experiences, will be compared in subjects who received a given dose of ABX464 or placebo by likelihood ratio chi-square test on a 10% two-sided significance level (*14.3.1.2.1*).

Two periods will be defined for TEAE:

- Period I: any adverse event which occurs or worsens from first dosing to Day 84;
- Period II: any adverse event which occurs after Day 84.

Adverse events will be described by primary system organ class and preferred term according to the two periods. Numbers and percentage of patients, and number of occurrences of adverse event will be presented for:

- TEAE (Table 14.3.1.2.2 and Table Table 14.3.1.2.3);
- Serious TEAE (Table 14.3.1.3.1 and Table Table 14.3.1.3.2);
- TEAE leading to drug discontinuation (Table 14.3.1.4.1 and Table Table 14.3.1.4.2);
- TEAE of grade 3 or 4 (Table 14.3.1.5.1 and Table Table 14.3.1.5.2);

Further assessment of safety will be based on the frequency of adverse events (with and without regard to causality) graded according to the CTC-AE Classification and also, the review of individual values for clinical laboratory data, vital signs and ECG focusing on the detection of abnormal values and PCSAs [potentially clinically significant abnormalities (PCSAs) determined upon investigator considerations].

Adverse events will be tabulated (counts and percentages) by group. All adverse events will be listed, and the data will be tabulated by body system/organ class. Adverse event tabulations will include all treatment emergent adverse events, which will be further classified by severity, and relationship to treatment and dose level.

All adverse events (AE) will be classified using the version of the MedDRA coding dictionary specified in the DHM.

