Events will be classified as treatment-emergent if they started or increased in severity on or after the first date and time of medication dosing at Visit 1 and up to study closure or withdrawal date. If an event start date is partial, then the start day, month, year or stop date will be used to determine if the event is treatment-emergent. If the classification of the AE cannot be determined from the data available, then the event will be considered treatment-emergent.

Treatment-emergent adverse events (TEAEs) will be further classified as follows:

Severe TEAEs: Severity classified as 'severe' (Common Toxicity Criteria [CTC] grade 3 or 4) or missing.

Serious TEAEs: Serious classified as 'yes' or missing.

Drug-related TEAEs: Relationship to study drug classified as 'related' or missing.

Serious drug-related TEAEs: Both serious and drug-related, as specified above.

TEAEs leading to withdrawal from study: Action taken classified as 'discontinued'.

All AE summary tables will show the number (%) of patients having at least one event and the number of events in each treatment group and overall. Median duration of AEs (from baseline to occurrence) will be presented in the tables. Note: If a patient has multiple AEs with the same preferred term, these will be summarised once within the count for N (%) of patients, but each event will be counted within the number of reports n of each AE. Changes in severity of the same AE (if collected) will be counted only once within the number of reports n of each AE.

The following will be presented in listing format within the data summaries:

- Deaths (Table 14.3.2.1);

- Serious Adverse Events (*Table 14.3.2.2*);
- Adverse Events which Led to Withdrawal (*Table 14.3.2.3*).

All adverse events (including non-treatment-emergent events) recorded on the CRF will be listed within the data listings.

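### RA progression is recorded as an adverse event and counted in the primary any-TEAE comparison, so it can dilute an ABX464 excess; a companion comparison without it should be prespecified

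*Protocol*

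**What the plan says.** Protocol section 7 sets the recording rule: "Any disease progression will be reported in the eCRF both as an adverse event and documented in the efficacy section".

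Protocol 2.3 makes TEAE incidence the primary endpoint, and SAP 4.1 repeats it: "incidence of treatment-emergent adverse events in the ABX464 treated Patients versus placebo, categorized by severity". The quantity tested is the all-TEAE rate. Protocol 8.6: "Primary safety endpoint is the rate of all treatment emergent adverse experiences". SAP 11.6.1: "the rate of all treatment emergent adverse experiences, will be compared in subjects who received a given dose of ABX464 or placebo", by likelihood-ratio chi-square at 10% two-sided. The shell for Table 14.3.1.2.1 (SAP section 15) shows this as yes or no per patient.

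The rule for what is treatment-emergent has no exception for the disease under study: "Events will be classified as treatment-emergent if they started or increased in severity on or after the first date and time of medication dosing" (SAP 11.6.1). The nearest exemption, in Protocol 7.3.1, covers only disease-associated abnormal findings that were present at the start and did not worsen.

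Neither document defines disease progression, gives an expected rate for it, or plans a TEAE comparison without it. Protocol 8.4 plans a summary of TEAEs recorded as possibly or probably related. SAP 11.6.1 defines drug-related TEAEs, but the table list in SAP 14.1 has no table for them.

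**The concern.** One event is used twice: once as worsening disease in the efficacy section, and once as a harm in the primary safety rate. In the any-TEAE count, an RA flare weighs the same as a headache or a skin lesion.

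Two consequences follow. First, progression at equal rates in both arms raises both TEAE rates and narrows the gap between them. Second, if ABX464 reduces worsening, progression raises the placebo rate more than the active rate and offsets part of any excess caused by the drug. Protocol 6.2 lists RA worsening among the reasons for discontinuation, so the plan expects that it may occur. A reader of the primary safety table could not tell how much of the contrast, or of its absence, comes from disease activity.

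**Working it through.** **Inputs from the documents.** Placebo TEAE rate 10%, ABX464 50%, likelihood-ratio chi-square at 10% two-sided, stated power 89% (Protocol 8.6). 20 patients per arm (Protocol 3.1.1).

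**Assumed inputs.** Progression rates by arm, taken as independent of other TEAEs. The documents give none.

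**Step 1: reproduce the stated power.** Normal approximation, pooled variance under the null:
- difference 0.50 − 0.10 = 0.40; mean rate 0.30
- SE under the null = √(0.30 × 0.70 × 2/20) = 0.145
- SE under the alternative = √(0.50 × 0.50/20 + 0.10 × 0.90/20) = 0.130
- power = Φ[(0.40 − 1.645 × 0.145)/0.130] = 0.892

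This agrees with the plan's 89%. Exact enumeration of all 21 × 21 outcomes, rejecting when the likelihood-ratio statistic exceeds 2.706, gives 0.912. The gap between 89% and 91% is a difference of method, not an error in the plan. The exact value is the reference below.

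**Step 2: add progression.** In each arm:

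observed TEAE rate = 1 − (1 − other-TEAE rate) × (1 − progression rate)

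For 20% on placebo and 5% on ABX464:
- placebo: 1 − 0.90 × 0.80 = 28%
- ABX464: 1 − 0.50 × 0.95 = 52.5%

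| Progression, placebo / ABX464 (assumed) | Observed TEAE, placebo v ABX464 | Difference (points) | Exact power |
|---|---|---|---|
| 0% / 0% | 10% v 50% | 40 | 91% |
| 5% / 5% | 14.5% v 52.5% | 38 | 86% |
| 10% / 10% | 19% v 55% | 36 | 80% |
| 10% / 5% | 19% v 52.5% | 33.5 | 76% |
| 20% / 20% | 28% v 60% | 32 | 66% |
| 20% / 5% | 28% v 52.5% | 24.5 | 49% |

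**Step 3: when would the excess vanish?** Set the two observed rates equal, with a the progression rate on ABX464 and p that on placebo:

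0.50 × (1 − a) = 0.90 × (1 − p), so p = 1 − 0.50 × (1 − a)/0.90

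- a = 0: p = 44%
- a = 5%: p = 47%
- a = 10%: p = 50%

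**Step 4: could the other planned outputs separate the two?** The SOC and preferred-term tables would show RA terms by arm. They do not show how many patients count as TEAE cases only because of RA worsening, since a patient with a flare and another event stays in the count either way. The adverse event listing (Listing 16.2.7) would allow that recount, but only with terms chosen after the results are known.

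**The case against.** The strongest reply is that the endpoint never claims to isolate toxicity. It is all-causality TEAE incidence, and Protocol 7.1 already counts a new or exacerbated disease as an AE, whether or not it is related to treatment. Drug-induced RA worsening would also be a safety signal in its own right, so removing it from the primary comparison could hide a harm. Both arguments stand, and they are why the all-TEAE comparison should remain primary.

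A second reply is that the p-values are descriptive (SAP 10.6) and that serious, grade 3 or 4, discontinuation and preferred-term tables are planned. This limits the weight of lost power. It does not remove the dilution of the estimate itself, and none of these tables gives a prespecified patient-level comparison without RA worsening.

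Three stronger readings are tempting, and the documents do not support them:
- **That lack of efficacy counts as an AE.** Only progression is recorded. A patient who misses ACR20 without worsening generates no event under this rule, and the planned ACR20 rates of 65% v 25% do not yield a progression rate.
- **That a true excess would be hidden.** In the most unequal row of the table, 24.5 points of excess still show. Step 3 gives the rates needed for full masking, and nothing in the documents suggests progression of that order over 12 weeks.
- **That the loss must be large.** At 5% in each arm, power drops only from 91% to 86%.

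**Conclusion.** The point holds as dilution. The recording rule, the any-TEAE test and the lack of any separating rule are all explicit in the text, so RA worsening enters the primary safety rate. The direction is clear when progression is equal in both arms or commoner on placebo: the ABX464 excess shrinks.

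The size is uncertain. The range from 86% down to 49% power rests wholly on assumed progression rates, on independence from other TEAEs, and on the plan's own 10% v 50%. This warrants a cheap addition to the SAP. It does not invalidate the primary endpoint.

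**What to change.** Keep the all-TEAE comparison as primary and keep recording RA worsening as an AE. Then:

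1. Define disease progression for AE reporting, so that the threshold does not vary across about 20 sites.
2. Identify these events by an eCRF flag, or by a preferred-term list fixed at the blinded data review before lock (SAP 9.4). Recruitment was ongoing when the SAP was written (SAP 1.1); the term list has the advantage of needing no eCRF change.
3. In SAP 11.6.1, prespecify a companion to Table 14.3.1.2.1: the same test and layout, excluding RA worsening, with the number of patients with RA worsening shown by arm beside it.
4. Add to SAP 14.1 the related-TEAE summary that Protocol 8.4 already plans.

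The cost is some SAP wording, one flag or term list, and one or two extra tables. No additional patients or visits are needed.

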7.1. Definition of an AE

Any untoward medical occurrence in a patient or clinical investigation patient administered a pharmaceutical product and which does not necessarily have to have a causal relationship with this treatment.

An AE can therefore be any unfavorable and unintended sign (including an abnormal laboratory finding), symptom, or disease (new or exacerbated) temporally associated with the use of a medicinal product, whether or not considered related to the medicinal product.

Note: The official definition also extends to AEs occurring in the placebo arm. Because of regulatory requirements, events occurring during pre-and post-treatment periods will also be designated as AEs. Therefore, reporting of such events, AEs and SAEs, will commence when the patient is enrolled into the study (date of signature of the informed consent) up until 4 Weeks after the end of the treatment visits. The period after discontinuing study drug may be extended if there is a strong suspicion that the drug has not yet been eliminated.

7.2. Definition of a SAE

A serious adverse event (experience) or reaction is any untoward medical occurrence that, at any dose:

- a) Results in death

NOTE: Death is an outcome of an AE, and not an AE in itself. Event which led to death should be recorded with fatal outcome.

- b) Is life-threatening

NOTE: The term 'life-threatening' in the definition of 'serious' refers to an event in which the patient was at risk of death at the time of the event. It does not refer to an event, which hypothetically might have caused death, if it were more severe.

- c) Requires hospitalization or prolongation of existing hospitalization

NOTE: In general, hospitalization means that the patient has been detained (usually involving at least an overnight stay) at the hospital or emergency ward for observation and/or treatment that would not have been appropriate in the physician's office or out-patient setting. Complications that occur during hospitalization are AEs. If a complication prolongs hospitalization or fulfills any other serious criteria, the event is serious. When in doubt as to whether "hospitalization" occurred, or was necessary, the AE should be considered serious.

Hospitalization for elective treatment of a pre-existing condition that did not worsen after informed consent was given is not considered serious.

- d) Results in persistent or significant disability/incapacity,

NOTE: The term disability means a substantial disruption of a person's ability to conduct normal life functions. This definition is not intended to include experiences of relatively minor medical significance such as uncomplicated headache, nausea, vomiting, diarrhea, influenza, and accidental trauma (e.g. sprained ankle) which may interfere or prevent everyday life functions but do not constitute a substantial disruption.

- e) Is a congenital anomaly/birth defect

- f) Is another medically important condition: This refers to an AE that may not be immediately life-threatening or results in death or hospitalization but may jeopardize the patient or may require

intervention to prevent one of the outcomes listed above. Based on medical and scientific judgment this should usually be considered serious.

If there is any doubt about whether or not an AE is serious, the investigator should contact the sponsor.

7.2.1. Events and/or Outcomes Not Qualifying as SAEs

Any hospitalization, or prolongation of hospitalization due to the circumstances listed below, will not be reported as SAE:

- planned medical/surgical procedure;
- planned medical/surgical admission (planned prior to entry into study, appropriate documentation required), for the disease under study;
- Administrative or social reasons (e.g. lack of housing, economic inadequacy, care-giver respite, family circumstances).

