2.4. Secondary Endpoints

Main Efficacy Endpoint:

- Proportion of patients achieving a categorical ACR20 response at Week 12.

The components of ACR20 assessment include:

- C-Reactive Protein (CRP) (mg/L),
- Tender/painful joint count (TJC) (28 joints),
- Swollen joint count (SJC) (28 joints),
- Patient assessment of joint pain (Pain-VAS),
- Patient global assessment of disease (PtGA),
- Physician's Global Assessment of Disease (PrGA),
- HAQ-DI

Other secondary endpoints:

- Change from Baseline in the following disease parameters at Week 2, Week 4, Week 8 and Week 12:
 - Individual components of the ACR20 response (CRP, TJC(28), SJC(28), Pain-VAS, PtGA, PrGA, HAQ-DI)
 - Erythrocyte Sedimentation Rate (ESR);

- DAS28-CRP and DAS28-ESR. The components of DAS28 assessment include TJC(28), SJC(28), CRP/ESR, and PtGA;
- SDAI score which includes TJC(28), SJC(28), CRP, PtGA, and PrGA;
- CDAI score which includes TJC(28), SJC(28), PtGA, and PrGA;
- Functional Assessment of Chronic Illness Therapy (FACIT)-Fatigue score
- Proportion of patients achieving at Week 2, Week 4, Week 8 and Week 12:
 - ACR20/50/70 response
 - Categorical DAS28-CRP response. Proportion of patients achieving categorical DAS28-CRP response will be measured as moderate/good European League Against Rheumatism (EULAR) response at each assessment time point;
 - Low Disease Activity (LDA) ($\text{DAS28} \leq 3.2$)
 - DAS28-ESR remission ($\text{DAS28} < 2.6$)
 - ACR/EULAR remission (TJC(28), SJC(28), CRP, and PtGA: $\text{all} \leq 1$);
 - SDAI remission ($\text{SDAI} \leq 3.3$);
 - CDAI remission ($\text{CDAI} \leq 2.8$).
- Concentration of miR-124 expression in total blood (determined by qPCR) at baseline and week 8
- Change from Baseline in miR-124 expression in total blood at Week 8
- PK parameters:
 - Pre-dose plasma concentration of ABX464/N-Glu at Week 2 and Week 8;
 - Post-dose plasma concentration of ABX464/N-Glu at 1-, 2- and 3-hours post-dose at Baseline, Week 2 and Week 8;
 - Trough plasma concentration of ABX464/N-Glu at End of Study Visit
- The number of incidences of treatment-emergent serious adverse events;
- The number of incidences of treatment-emergent adverse events of special interest;
- The number of incidences of adverse events leading to investigational product discontinuation;
- The number of incidences of clinically significant laboratory abnormalities;
- The number of incidences of all AE (causally related and non-related) and SAE, further categorized by severity.

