7.4. Time Period, and Frequency of Detecting AEs and SAEs

All AEs and SAEs occurring from the time a patient consents to participate in the study until 4 Weeks after he or she has completed or discontinued the investigational product must be recorded in the Patient's eCRF.

Moreover, any occurrence of pregnancy within 6 months post stopping dosing must be reported.

Importantly, SAEs will have to be reported, either by email or by Fax, to IntuVigilance Limited within 24 hours of awareness of an SAE.

IntuVigilance Limited

[name]

Hotline [contact]

Email Address: [contact]

[contact]

Legislative guidance requires the investigator to also ensure that any **related** SAEs are reported after the patient finished the study if the investigator becomes aware of them.

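### The planned-procedure exemption in Protocol 7.2.1 omits the conditions set in 7.2(c), so an on-study event that is serious only through a scheduled admission need not be reported as an SAE

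*Protocol*

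**What the plan says.** Protocol 7.2 lists the seriousness criteria. Criterion (c) is "Requires hospitalization or prolongation of existing hospitalization". The note under it gives one exemption for elective care: "Hospitalization for elective treatment of a pre-existing condition that did not worsen after informed consent was given is not considered serious". The same note deals with complications: "If a complication prolongs hospitalization or fulfills any other serious criteria, the event is serious".

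Protocol 7.2.1 then lists hospitalizations that do not count: "Any hospitalization, or prolongation of hospitalization due to the circumstances listed below, will not be reported as SAE". There are three circumstances:

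- First bullet: "planned medical/surgical procedure", with nothing further.
- Second bullet: "planned medical/surgical admission (planned prior to entry into study, appropriate documentation required), for the disease under study".
- Third bullet: administrative or social reasons. This bullet is not in question here.

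Protocol 7.4 requires recording of "All AEs and SAEs occurring from the time a patient consents to participate in the study", until 4 weeks after the investigational product is completed or stopped. Protocol 2.4 includes as a secondary endpoint "The number of incidences of treatment-emergent serious adverse events". SAP 11.6.1 counts a treatment-emergent event as serious when the recorded seriousness field is yes or missing.

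**The concern.** The two sections draw the line in different places. Section 7.2(c) ties its exemption to the state of the condition: it existed before and has not worsened since consent. The first bullet of 7.2.1 ties it only to the fact that a procedure was planned. An admission arranged during the study to investigate or treat something that began on study is, in ordinary language, for a planned procedure.

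Three things depend on the SAE classification:

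- the report within 24 hours (Protocol 7.4 and 7.6);
- the DSMB's review, within 7 days, of SAEs that may be causally related (Protocol 3.1.3);
- the treatment-emergent SAE count (Protocol 2.4) and the serious-event tables in the SAP.

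The SAP takes the site's classification as recorded, so its serious-event rule does not recover an event entered as not serious. With approximately 20 sites, the same admission could also be classified in opposite ways, depending on which section a site follows.

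**Working it through.** The plan gives no figure to reproduce, so the check compares the texts.

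**Step 1. Conditions attached to each exemption.**

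| Condition | 7.2(c) note | 7.2.1, first bullet | 7.2.1, second bullet |
|---|---|---|---|
| Elective treatment | yes | only that the procedure is planned | only that the admission is planned |
| Pre-existing condition | yes | not stated | limited to the disease under study |
| No worsening after consent | yes | not stated | not stated |
| Planned before study entry, with documentation | not stated | not stated | yes |

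The first bullet lacks both limits that 7.2(c) places on the condition. The second bullet carries an explicit limit on when the admission was planned, so the drafters wrote such a limit where they attached one. The first bullet has none.

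**Step 2. Does any other text limit the first bullet?** The other parts of Protocol section 7 (reporting period, recording, SAE reporting and regulatory reporting), the DSMB text in 3.1.3 and section 7 of the SAP, and SAP 11.6.1 were checked. None does.

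**Step 3. Test case.** Suppose a condition first appears, or worsens, after consent. An admission is scheduled during the study to treat or investigate it, and no other seriousness criterion is met.

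- Under 7.2(c): hospitalization was required. The exemption fails because the condition is new or has worsened. The event is serious.
- Under 7.2.1, first bullet: the hospitalization is for a planned procedure. It is not reported as an SAE.

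The same event is classified differently by the two sections.

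**Step 4. Which outputs use the classification?**

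- They do: the 24-hour report, the 7-day DSMB review of potentially related SAEs, and the treatment-emergent SAE count.
- They do not: the primary endpoint (TEAE incidence by severity, Protocol 2.3; tested in SAP 11.6.1 as the rate of any TEAE), the grade 3 or 4 TEAE tables, and the dose-limiting toxicity rule in Protocol 3.1.2, which uses CTC-AE grade and causality.

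**Step 5. Scale.** With 20 patients planned per arm and 40 on active drug, one patient whose only SAE is missed changes the arm's proportion by 1/20 = 5 percentage points, or the pooled active proportion by 1/40 = 2.5 points. This is true of any misclassified patient. It says nothing about how often the situation would arise, and the documents give no SAE rate from which to estimate that.

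**The case against.** The strongest reply is that 7.2.1 is a subsection of 7.2 and should be read with it. An admission required by a new event can be seen as due to that event rather than to the procedure. Section 7.2 also has safeguards: doubt about whether a hospitalization occurred or was necessary is resolved towards serious, the investigator contacts the sponsor when seriousness is uncertain, criterion (f) covers medically important events, and complications that prolong a stay are serious.

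These points narrow the gap but do not close it. The doubt rule does not address whether an admission was planned, and 7.2.1 is worded as a flat instruction, so a site following it may feel no doubt. The complication rule covers only what happens during a stay. An event whose sole claim to seriousness is a scheduled admission remains exposed.

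Several stronger readings are tempting but not supported:

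- A reader might infer that 7.2(c) requires the procedure to have been planned and documented before consent. It does not; planning before entry and documentation appear only in the second bullet of 7.2.1. The conflict with 7.2(c) concerns elective treatment, pre-existence and non-worsening.
- A reader might infer that a pre-planned RA admission is an SAE under 7.2 whenever RA worsens on study. Losing the exemption is not the same as meeting criterion (c). If the admission goes ahead as already arranged, the worsening did not necessarily require it.
- A reader might infer that every admission outside the narrowed bullets should be reported as an SAE. That would contradict 7.2(c), which does not treat elective care scheduled after consent for an unchanged pre-existing condition as serious, and would override the administrative and social exemption.

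**Conclusion.** The contradiction is real and in the current text. The first bullet of 7.2.1 is wider than the exemption in 7.2(c), and nothing else in the protocol or SAP limits it. This rests on the literal wording of that bullet; a site that carried the 7.2(c) conditions into it would classify the event correctly, but the text does not tell it to.

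The consequence is bounded. The treatment-emergent SAE count, the 24-hour report and the 7-day review are exposed, the last only for potentially related SAEs. Because the primary objective is safety, a reader might infer that the primary result is affected. It is not: the event is still recorded as an AE and still counts as a TEAE if it is treatment-emergent, and the primary endpoint makes no use of seriousness. Routine DSMB meetings also take place monthly. The number of affected events cannot be derived from the documents and may be zero. The change is still worthwhile because it costs almost nothing and gives sites one rule for a safety count in a small trial.

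**What to change.** Reconcile Protocol 7.2 and 7.2.1 as follows:

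1. Limit the planned-procedure and planned-admission bullets of 7.2.1 to the exemption already in 7.2(c): elective treatment of a pre-existing condition that has not worsened since informed consent.
2. Keep the second bullet's existing limits on pre-study planning and documentation.
3. Leave the administrative and social bullet unchanged.
4. Add a sentence stating that an adverse event which arises or worsens after consent, and which requires or prolongs hospitalization, is reported as an SAE even if the admission was scheduled.

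Do not add a catch-all making every other admission an SAE.

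The cost is a wording change to two bullets, one added sentence, and at most a few more SAE reports. The analysis rules in the SAP need no change, since they use the recorded seriousness field.
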